| Exclusion Criteria | 
 • Women that are pregnant or breast feeding. • Age <18 |

| | |
|----------------------------|--|
| | 
 • Severe kidney dysfunction (GFR <30 mL/min/1.73m²) |
| Treatment Description | ¹⁸ F-DCFPyL whole body PET/CT or PET/MR scan |
| Study Procedures | 
 • ¹⁸F-DCFPyL whole body PET/CT imaging for dosimetry studies; PET/MR scan to achieve other aims • Review of relevant imaging and medical record information |
| Statistical Considerations | 
There are no formal hypothesis tests planned.
 
Our primary goals are to:
 
 1. Record the normal biodistribution and radiodosimetry of PSMA in the body 2. Record the frequency the normal fallopian tubes and ovarian are seen on high resolution MR imaging. 3. Record the distribution of PSMA in cancer tissue 4. Estimate the frequency with which PSMA PET and MR imaging and final IHC staining disagree in their classifications of presence of disease. We will classify each data point as either an agreement or disagreement between imaging findings and IHC staining. The proportion of disagreements across all time points will be estimated with an intercept-only GEE regression model that accounts for correlation among measures from the same patient. This proportion will be reported with a 95% confidence interval. The lower bound of this confidence interval will be used to help us decide whether this approach is worthy of future study. Based on this pilot study we plan to pursue further evaluation in larger more appropriately powered studies if the lower bound of the confidence interval excludes 20%, which is chosen as a guideline to determine whether the method shows promise. |

SCHEMATIC OF STUDY DESIGN

Subject Populations

1.0 PROJECT SUMMARY:

The purpose of our proposal is to use PSMA PET and multi-parametric MR imaging, to detect the presence of gynecological cancer cells in the body. Imaging evaluation would include the appearance of normal ovaries/fallopian tubes, and cancerous tissue on different MR sequences and the distribution of PSMA in normal and pathological tissues on PET images. To determine the accuracy of the PSMA PET imaging localization in malignant tissues, PSMA staining of surgical pathology specimens will be used as the reference standard.

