3.0 STUDY AIMS/STUDY OBJECTIVES

The primary outcome of this research is to evaluate whether a novel imaging approach using PSMA-based ¹⁸F-DCFPyL PET and MR imaging can accurately determine the presence or absence of cancer, the accurate distribution of cancer and the normal biodistribution of PSMA in the abdomen and pelvis on PET imaging. The reference standard for the PSMA localization in cancerous tissue will be histologic and immunologic correlation on the pathologic specimens obtained at the time of standard of care surgical resection for treatment of the gynecological cancer. Specific aims for this research include the following:

1. To establish the biodistribution and radiodosimetry of PSMA-based ¹⁸F-DCFPyL on PET imaging in normal female controls and in females with known or suspected cancer.
2. To determine the sensitivity, specificity, and accuracy values of PSMA-based ¹⁸F-DCFPyL PET and MR imaging in the detection of cancer in women with known or suspected gynecologic malignancy and differentiating cancerous tissue from non-cancerous tissue. The performance of PSMA-based ¹⁸F-DCFPyL PET imaging in the detection and localization of cancerous and non-cancerous tissue will be compared to the final surgical pathology reports and to the histological and immunostaining for PSMA positive cancerous tissue on pathology.
3. To determine the most accurate approach in assessing disease burden and location, assessment of tumor burden on both the PSMA-based ¹⁸F-DCFPyL PET and MR imaging

together, and then each modality separately will be performed and sensitivity, specificity, and accuracy values will be calculated.

4.0 RESEARCH DESIGN AND METHODS:

Subject population

Fifty-two subjects will be enrolled in this research, 12 healthy controls and 40 patients with known or suspected gynecologic cancer. Up to 6 subjects will be used for the dosimetry portion. Eligibility requirements include the following:

Inclusion Criteria for healthy female controls N=12 (includes up to 6 Dosimetry subjects)

1. Women with no suspected gynecological cancer
2. No contraindications for MR or PET imaging
3. Greater than or equal to 18 years of age
4. Scheduled to undergo a hysterectomy and/or salpingo-oophorectomy

Inclusion Criteria for female controls (Dosimetry)

1. Women with or without suspected gynecological cancer
2. No contraindications for MR or PET imaging
3. Greater than or equal to 18 years of age

Inclusion Criteria for gynecologic cancer patients N=40

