A member of the study team will follow-up with all subjects approximately 1 to 3 days, by phone, after their PET/MRI or PET/CT exam to inquire about delayed side effects. If the subject is experiencing any late occurring side effects, they will be asked to return to the research clinic for a follow-up exam.

All PET and MR hardware are FDA approved as are the PET and MR sequences to be used.

Histopathological, Immunologic Staining and Image Correlation

We will correlate the final surgical pathology report with the images to determine if all sites of disease were seen on PSMA PET and MR imaging. In addition to this, we will identify very specific sites (eg. Left obturator node; Right ovarian mass; etc) for PSMA immunologic staining pre-operatively by review of the imaging between the radiologist and the gynecologic oncology surgeon and the surgeon will make every attempt to send these PSMA specimens labeled and separate from the other specimens obtain during surgery.

The surgical pathology specimens will be processed per routine clinical protocol. The same tissue blocks used for routine pathological evaluation will be used for the immunolabeling of the PSMA in the TRIP lab. After the clinical processing is complete, the pathologist will choose the appropriate tissue block(s) for immunolabeling, which consumes only a minute amount of tissue. This process will in no way compromise patient care.

Review of Medical Records

Medical records will be reviewed to obtain medical history including physical exams, medications, laboratory tests, imaging results and any other information related to the diagnosing, treatment, or outcomes of subjects diagnosis.

Remuneration

Subjects will receive \$100 as compensation for their participation in this study.

Study Withdrawal

Reasons for withdrawal or termination

Enrolled patients will be removed from the study in the following circumstances:

- The patient does not complete the imaging examinations per study protocol
- The subject withdraws consent
- Exclusion criteria are discovered after registration but prior to the research examinations
- The patient has a contrast reaction to the gadolinium based contrast agent utilized for the MRI
- The PI or co-investigators determine it is within the best interest of the subject to remove them from the research.

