10.0 STATISTICAL CONSIDERATIONS

The goals of this study are to 1) record the normal distribution of PSMA in the body, 2) record the frequency that the normal fallopian tubes and ovarian are seen on high resolution MR imaging, 3) record the distribution of PSMA in cancer tissue, and 4) estimate the sensitivity, specificity, and accuracy of PSMA PET and MR imaging.

12 healthy controls and 40 subjects with known gynecologic cancer will be enrolled in this pilot study. With final IHC staining as the “gold standard” in detection of cancer, we will estimate the sensitivity, specificity, and accuracy of PSMA PET and MR imaging. The sample size was chosen based on logistical and financial considerations. The table below shows the precision with which we will be able to estimate the sensitivity and specificity of PSMA PET and MR imaging.

| Sensitivity/Specificity | Width of 95% CI |
|-------------------------|-----------------|
| 65% | 31.1% |
| 70% | 29.9% |
| 72.5% | 29.3% |
| 75% | 28.5% |
| 77.5% | 27.7% |
| 80% | 26.5% |
| 82.5% | 25.5% |
| 85% | 24.1% |

Based on this pilot study, we plan to pursue further evaluation in larger, more appropriately powered studies if sensitivity and specificity are at least 80%.

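### Section 10 judges cancer detection against PSMA staining alone, on sites picked from the study images, and never carries Aim 2's surgical pathology comparator into an estimate

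*Combined protocol and SAP*

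**What the plan says.** Section 10 sets the reference: "With final IHC staining as the “gold standard” in detection of cancer", the plan will estimate sensitivity, specificity and accuracy of PSMA PET and MR imaging. Larger studies are to follow "if sensitivity and specificity are at least 80" percent. The only precision statement is a table of interval widths, introduced as follows: "The table below shows the precision with which we will be able to estimate the sensitivity and specificity of PSMA PET and MR imaging".

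Section 10 does not say which IHC stain it means. That it is PSMA is an inference from Section 1.0 and from the staining procedure in Section 5.0. Section 1.0 gives the stain a narrower role, concerning the "accuracy of the PSMA PET imaging localization in malignant tissues, PSMA staining of surgical pathology specimens will be used as the reference standard". Section 3.0 is narrower still: "The reference standard for the PSMA localization in cancerous tissue will be histologic and immunologic correlation on the pathologic specimens".

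Section 5.0 (histopathology and image correlation) says that specific sites will be identified "for PSMA immunologic staining pre-operatively by review of the imaging between the radiologist and the gynecologic oncology surgeon". After clinical processing, "the pathologist will choose the appropriate tissue block(s) for immunolabeling". No rule covers sites that look negative on imaging.

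Surgical pathology does appear in the plan. Aim 2 (synopsis and Section 3.0) names the final surgical pathology reports as a comparator alongside staining, and Section 5.0 says: "We will correlate the final surgical pathology report with the images to determine if all sites of disease were seen". Neither Section 10 nor the synopsis statistics uses those reports in an estimate. The synopsis disagreement proportion also compares imaging with IHC, using a GEE model for repeated measures within a patient.

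**The concern.** There are two separate problems, and both bear on the 80% rule.

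- **Reference.** PSMA staining answers whether the tracer's target is in the tissue; pathology answers whether the tissue is cancer. Read literally, Section 10 scores a PSMA-negative cancer as disease-free. An MR scan that correctly shows it becomes a false positive, and a PET scan that misses it becomes a true negative. That could distort Aim 3's comparison of PET, MR and both together.
- **Selection.** The images under test help to decide which tissue receives the reference test. If imaging-negative sites are stained less often than imaging-positive ones, this is partial verification: false negatives and true negatives drop out, so observed sensitivity rises and observed specificity falls.

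At stake is the decision on larger studies, which could be wrong in either direction, and an Aim 2 comparison that the statistical section does not deliver.

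**Working it through.** **1. The plan's own figures.** Exact (Clopper-Pearson) 95% intervals with n=40:

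| Sensitivity or specificity | Width in Section 10 | Exact, n=40 |
|---|---|---|
| 65% | 31.1 | 31.1 |
| 70% | 29.9 | 30.0 |
| 72.5% | 29.3 | 29.3 |
| 75% | 28.5 | 28.5 |
| 77.5% | 27.7 | 27.6 |
| 80% | 26.5 | 26.6 |
| 82.5% | 25.5 | 25.4 |
| 85% | 24.1 | 24.1 |

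All rows agree to about 0.1 point; n=52 would give 27.2 down to 21.0. The table therefore fits 40 independent units, the number of women in the cancer cohort. Section 5.0, however, works by site, and the synopsis expects several measures per patient. Section 10 names no unit.

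**2. Reference (assumed inputs).** Let g be the share of cancer sites that are PSMA-positive. Suppose imaging detects 90% of those and 10% to 20% of PSMA-negative cancers. If PSMA-positive stained sites are all cancer, sensitivity against staining is 90%. Against pathology it is g × 0.90 + (1 − g) × (0.10 to 0.20):

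- g = 0.9: 82% to 83%
- g = 0.8: 74% to 76%
- g = 0.6: 58% to 62%

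The choice of reference alone can move the result across 80%.

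**3. Selection (per site, combined PET and MR read).** Let f be the chance that an imaging-negative site is stained, relative to an imaging-positive site. The documents give no value, so a range is shown.

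- Observed sensitivity = Se / (Se + f(1 − Se))
- Observed specificity = f·Sp / (f·Sp + 1 − Sp)

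| True Se/Sp (%) | f | Observed Se/Sp (%) |
|---|---|---|
| 85/90 | 0.75 | 88.3/87.1 |
| 85/90 | 0.50 | 91.9/81.8 |
| 85/90 | 0.25 | 95.8/69.2 |
| 75/90 | 0.60 | 83.3/84.4 |

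**4. When the 80% rule is met.** Observed specificity reaches 80% when f ≥ 4(1 − Sp)/Sp. Observed sensitivity reaches 80% when f ≤ 0.25·Se/(1 − Se).

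- True 85/90, a method that should pass: lower limit 4 × 0.10/0.90 = 0.44; upper limit 0.25 × 0.85/0.15 = 1.42, which never binds for f up to 1. It fails for f below about 0.44.
- True 75/90, a method that should not pass: lower limit 0.44; upper limit 0.25 × 0.75/0.25 = 0.75. It wrongly passes for f of about 0.44 to 0.75.
- True 75/95 wrongly passes for f of 0.21 to 0.75, and true 60/95 for f of 0.21 to 0.375.

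**5. Unequal rates.** Let fD and fN be the relative rates for diseased and non-diseased imaging-negative sites. With fD = 1 and fN = 0.25, true 85/90 appears as 85.0/69.2 and fails. With fD = 0.25 and fN = 1, true 60/81 appears as 0.60/(0.60 + 0.25 × 0.40) = 85.7%, with specificity still 81%, and passes.

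**The case against.** - **Imaging-negative sites may well be stained.** This stands as a possibility. Review of the images can name negative sites, MR can add sites that PET misses, the pathologist chooses the blocks, and controls scheduled for surgery could supply negative tissue. For PET alone the bias may be smaller: if half of PET-negative sites are MR-positive and stained like PET-positive ones, with f = 0.25 for the rest, the effective f is 0.5 + 0.5 × 0.25 = 0.625, and true 85/90 appears as 90.1/84.9. A reader might infer that imaging-negative tissue goes unstained; the documents do not say so. The gap is that nothing ensures or records its staining.
- **Surgical pathology is already in the plan.** Correct: Aim 2 names it and Section 5.0 puts that correlation first. To say the comparison is absent would go too far. What is missing is any estimate, interval or decision rule in Section 10 that uses it.
- **PSMA may mark nearly all of these cancers.** Section 2.0 cites a pathology study reporting high and specific expression in ovarian and uterine tumour vessels. If so, the reference problem shrinks (82% to 83% against 90% when g = 0.9). The documents give no PSMA-positive share, and Section 11.0 notes high expression in normal kidney tubules.
- **The table suggests a per-woman analysis.** It does fit 40 women, and the per-site formulas do not carry over directly. A reader might then infer that the selection problem vanishes because every patient has surgery. That does not follow: Section 4.0 also admits women already operated on, and tissue removed before the scan cannot verify it. Section 10 gives no rule for combining sites into one call per woman, and PSMA staining would still stand in for cancer.
- **It is a pilot with no formal tests.** True, and this limits the weight of the point. The 80% rule is nevertheless the stated basis for going further.

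**Conclusion.** The point holds as a cheap improvement to Section 10. The reference named there is narrower than Aim 2 and answers a different question from cancer detection, and the site selection in Section 5.0 leaves room for partial verification.

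The size is unknown. The figures for f and g are assumptions, and those for f apply only to a per-site analysis. Within that frame the 80% rule can fail a good method (85/90 for f below about 0.44) or pass one that falls short (75/90 for f of about 0.44 to 0.75). A reader might infer that the error runs mainly one way, with wrong passes confined to a narrow band. The arithmetic does not support that: the band is narrow for true 60/95 but wide for 75/95, and it changes again when diseased and non-diseased sites are stained at different rates.

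No conclusion is drawn about the synopsis's 20% guideline, which rests on a confidence bound not computed here.

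**What to change.** In Section 10:

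1. Estimate sensitivity, specificity and accuracy for PET, MR and both combined against the final surgical pathology report, over all sites resected after the study scan, whatever the imaging result. Base the 80% rule on these estimates.
2. State the unit: per site with clustering by woman (the synopsis already plans GEE), or per woman with a rule for combining sites.
3. Report PSMA staining, including the synopsis disagreement proportion, separately as tracer concordance, with counts of imaging-positive and imaging-negative sites stained.
4. Exclude women whose only surgery preceded the scan from the pathology-based estimates, or report them separately.
5. State as a limitation that the surgeon sees the images before operating, so which sites are resected may itself depend on imaging.

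The cost is Section 10 wording and a per-site data form. The pathology reports are already to be correlated with the images, so no extra procedure or stain is needed. The downsides are more data entry, fewer evaluable women if some had earlier surgery, results limited to resected sites, and some remaining image-driven selection. Precision will depend on how many pathology-positive and pathology-negative units there are: at an observed 80%, the exact interval is 26.6 points wide with 40 independent units, 30.9 with 30 and 37.9 with 20.

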6.0 RISKS AND BENEFITS

PET:

Detailed organ dosimetry derived from four representative patients is included in the table below. Of note, the effective dose from ¹⁸F-DCFPyL was 0.0165 mSv/MBq or 6.1 mGy (0.61 rem) for an injected dose of 370 MBq (10 mCi), or 5.49 mGy or 5.49 mSv (0.549 rem) for 333 MBq (9 mCi) which is the highest dose administered for this study.

Dosimetry:

Highest radiation dose was estimated for the kidneys (0.0945 mGy/MBq) followed by urinary bladder wall (0.0864 mGy/MBq), submandibular glands (0.0387 mGy/MBq) and liver (0.0380 mGy/MBq). The mean absorbed dose to the bone marrow was 0.01 mGy/MBq. In comparison to the published data on our first generation agent, ¹⁸F-DCFBC, ¹⁸F-DCFPyL shows significantly lower (under 50 %) doses in most radiosensitive organs such as the thymus, ovaries, red marrow and osteogenic cells. Less radiation dose was also measured in lower large intestinal wall, small intestine, stomach wall, lungs, muscle and skin. Radiation dose from the two radiotracers was similar (within +/-50 %) in the gallbladder wall, upper large intestinal wall, spleen, testicles, thyroid, and pancreas. Radiation dose from ¹⁸F-DCFPyL was higher in the adrenals, kidneys, liver, pancreas, spleen, and bladder wall.

| Organ | Absorbed Dose (mGy/MBq) | Organ | Absorbed Dose (mGy/MBq) |
|----------------------|-------------------------|----------------------|-------------------------|
| Adrenals | 3.11E-02 | Ovaries | 8.89E-03 |
| Brain | 2.19E-03 | Pancreas | 2.44E-02 |
| Breasts | 4.57E-03 | Parotid Glands | 2.68E-02 |
| Gallbladder Wall | 1.44E-02 | Red Marrow | 1.04E-02 |
| Heart Wall | 1.29E-02 | Skin | 4.05E-03 |
| Kidneys | 9.45E-02 | Small Intestine | 9.13E-03 |
| Lacrimal Glands | 3.50E-02 | Spleen | 1.85E-02 |
| Lens | 1.25E-03 | Stomach Wall | 1.16E-02 |
| Liver | 3.80E-02 | Submandibular Glands | 3.87E-02 |
| LLI Wall | 1.05E-02 | Testes | 1.01E-02 |
| Lungs | 1.08E-02 | Thymus | 5.56E-03 |
| Muscle | 6.32E-03 | Thyroid | 8.56E-03 |
| Osteogenic Cells | 9.58E-03 | ULI Wall | 1.67E-02 |
| Urinary Bladder Wall | 8.64E-02 | Uterus | 1.15E-02 |

CT:

Low-dose CT imaging is used to provide attenuation correction for the PET scan and PET signal localization. The addition radiation dose associated with this imaging is approximately 1.0 rem or 10 mSv. For the dosimetry PET/CT scans, there will be two low-dose CT scans obtained for a total of approximately 2.0 rem or 20 mSy.

MR:

Because the MR scanner is comprised of a very strong magnet, the primary risk associated with MRI imaging is the risk of having ferrous metal in the body such as pins, rods, screws, pacemakers, etc.

Risks will be minimized by making subjects feel as comfortable as possible in the PET/MR scanner. They will be repositioned and provided with as much padding as needed. Subjects will be able to communicate with the imaging staff in the event they decide they cannot continue to lie still for the duration of the study, in which case the study procedure will be terminated. Potential subjects who are asked to participate in MR imaging will be screened for contraindications to MRI and gadolinium contrast.

Gadolinium based contrast agents: Gadobenate dimeglumine be administered according to a weight-based algorithm (0.1 mmol/kg), not to exceed 20 mL. The risks of administering a gadolinium-based agent are exceedingly low; common side effects may include headache, nausea, reaction at injection site, and vasodilatation (temporary widening of a blood vessel) that occurred in less than 3% of subjects. Other less-common side effects reported were bad taste in the mouth, skin rash, dizziness, or warm tingling or burning feeling on the skin.

Acute allergic reactions are extremely uncommon, far less common than occur with iodine-based contrast agents used in CT scanning. To treat unexpected contrast reactions, we maintain a fully up-to-date contrast reaction/resuscitation kit adjacent to our scanners in the UWHC Department of Radiology. The contrast reaction kit is identical to those used throughout our department to treat allergic reactions to iodinated contrast or gadolinium based contrast agents, and is fully stocked with all necessary medications to treat contrast reactions. Further, there is always an experienced radiologist who is trained in treating contrast reactions available within the UWHC during working hours, for this purpose.

There are no immediate benefits anticipated for the participants. This research has a long-term benefit of validating the feasibility of a PET/MR imaging technique with enhanced diagnostic, prognostic and treatment response monitoring capabilities. Ultimately, this trial may allow us to perform PET scans in a much shorter period of time and achieve better quantification.

Glucagon: Contraindications to glucagon include known hypersensitivity to the drug, known pheochromocytoma or insulinoma. Subjects that are diabetic will not be given this drug. The nurse administering glucagon will screen subjects for a history of diabetes prior to its administration. Glucagon is typically well tolerated and is rapidly metabolized with a half-life of approximately 8-18 minutes.

Blood Collection: The blood sample will be collected via IV. Subjects may experience some discomfort, minor bruising, bleeding, or inflammation in the area where the blood is drawn. They may also experience nausea, lightheadedness, or fainting associated with this blood draw. There is also a very small chance (less than 1%) of infection at the needle puncture site.

7.0 ADVERSE EVENTS AND SAFETY ISSUES

Definition of adverse events and potential risks: The term “adverse event” is defined in the International Conference on Harmonization Guideline for Good Clinical Practice as follows: “Any untoward medical occurrence in a patient or clinical investigation subject administered a pharmaceutical product and which does not necessarily have a causal relationship with this treatment. An adverse event (AE) can therefore be any unfavorable and unintended sign (including an abnormal laboratory finding), symptom, or disease temporally associated with the use of a medicinal (investigational) product whether or not related to the medicinal (investigational) product”.

Medical conditions of a subject that exist prior to receiving the investigational imaging tracer will be recorded as medical history. After administration of the investigational imaging tracer, all new medical conditions are considered adverse events. Adverse events occurring in this trial will be recorded in data collection forms, regardless of whether or not they are thought to be associated with the investigational imaging tracer throughout the study period. However, the Investigator also will assess the possible relationship between the adverse event and the investigational imaging tracer.

For the purposes of this protocol, an adverse event (AE) is any untoward medical occurrence (e.g., sign, symptom, disease, syndrome, intercurrent illness, abnormal laboratory finding) that emerges or worsens relative to pre-imaging baseline. We anticipate minimal adverse effects or toxicity with the investigational imaging tracer ¹⁸F-DCFPyL in this study.

Definition of Serious Adverse Events (SAE), SAE list: Any adverse drug experience, occurring at any dose that results in any of the following:

- Death
- Is life-threatening (an event in which the patient was at immediate risk of death; it does not refer to an event which hypothetically might have caused death if it were more severe)
- Requires or prolongs inpatient hospitalization
- Results in a persistent or significant disability/incapacity
- Is a congenital anomaly/birth defect
- Important medical events that may not result in death, be life-threatening, or require hospitalization may be considered serious when, based upon appropriate medical judgment, they may jeopardize the patient or subject and/or may require intervention to prevent one of the outcomes listed.

All other AEs will be treated as “non serious” and are described in the final study report. An SAE that is definitely, probably or possibly related to the investigational imaging tracer will be reported immediately (within 24 hours of its determination) by telephone or fax by the Principal Investigator.

AE Characteristics: Toxicity will be graded according to the NCI Common Toxicity Criteria (CTCAE), version 4.03 (Appendix A; which can also be accessed and downloaded via the website: <http://ctep.cancer.gov/reporting/ctc.html>). The Investigators will monitor the occurrence of adverse events during the course of each patient in the study. The Investigators need to assess whether there is a reasonable possibility that the study imaging agent caused or contributed to an AE using the following criteria as a guide:

- **Definite:** The adverse event is clearly related to the investigational agent.
- **Probable:** There is a clinically plausible time sequence between the onset of the AE and administration of imaging tracer. The AE is unlikely to be caused by the concurrent/underlying illness, other drugs, or procedures.
- **Possible:** There is a clinically plausible time sequence between the onset of the AE and administration of imaging tracer, but the AE could also be attributed to the concurrent/underlying disease, other drugs, or procedures. “Possibly” should be used when the administration of the study imaging tracer is one of several biologically plausible causes of the AE.
- **Unlikely:** The adverse event is doubtfully related to the investigational imaging tracer.
- **Not Related:** Another cause of the AE is the most plausible and/or a clinically plausible temporal sequence is inconsistent with the onset of the AE and the investigational imaging tracer; and/or a causal relationship is considered biologically implausible.

If any adverse event is considered to be definitely, possibly or probably related to the investigational imaging tracer, that event will be followed until resolution or until it is deemed chronic or irreversible by the Investigator. If an event is unlikely or not related to the investigational imaging tracer, the event will not be reported.

All AE will be documented and recorded in the medical record and will include:

- I. Specific reaction according to NCI Common Toxicity Criteria, version 4.0.
- II. Duration of the reaction
- III. Severity/grade according to NCI Common Toxicity Criteria, version 4.03. If the adverse event is not addressed by the Common Toxicity Criteria, the severity should be rated as mild (grade 1), moderate (grade 2), severe (grade 3), or life threatening (grade 4).
- IV. Relation of reaction to study agent

V. Management of reaction, including any interruption or dose modification of the study drugs.

Event Severity: In addition to classifying an adverse event as serious or non-serious, the Investigator and/or designated personnel will grade the adverse event to describe the Maximum intensity of the event. Specific criteria for the intensity of adverse events are described in the Common Toxicity Criteria (CTC: National Cancer Institute). Investigators should follow these criteria for grading and reporting adverse events.

An event may be severe, but may not be serious (e.g., severe headache). The severity of an adverse event will be assessed by study personnel using their best clinical judgment and includes but is not limited to taking into account the patient's past history, the patient's chart, interviews with the patient and caregivers, and direct observation. The Investigator will also be asked to assess the possible relationship between the adverse event and the administration of the investigational imaging tracer.

Adverse Event Reporting: Per 21CFR312.32(c), all adverse events deemed both serious and unexpected associated with the use of the drug must be reported to the FDA and to all participating investigators as soon as possible and in no event later than 15 days.

The FDA will be notified of any unexpected fatal or life threatening experience associated with the drug as soon as possible but in no event later than 7 calendar days. The UW HS-IRB will be notified in accordance with posted institutional policy.

Adverse Events: Serious and Non Serious Adverse events will be recorded, regardless of whether or not they are thought to be related to the investigational imaging tracer. While all adverse events will be tabulated and reported in the study final report, serious adverse events will be reported in the course of the trial. Adverse events that meet criteria of a serious adverse event listed above will also be recorded and reported.

The Investigator will inform the IRB of all adverse events attributed to the investigational imaging tracer in accordance with posted institutional policy.

